12.3. Statistical analysis

A detailed statistical analysis plan (SAP) will be described in a separate document. The plan might be reviewed and updated as result of the review of the data before database locking.

12.3.1. Descriptive Statistics

General descriptive statistics for numeric variables will include the n (number of observed values), the mean, the standard deviation, 95% CI, the median, the minimum, and the maximum values. For categorical variables, the number and percent of subjects with a specific level of the variable will be presented.

12.3.2. Missing data

Details on dealing with missing data, along with the handling of possible outliers, will be described in the SAP. Critical missing data, if any, will be discussed during the review of the data before database locking. Decisions will be fully documented in the Data Review Report.

12.3.3. Description of the population-description of baseline characteristics

Demographics and baseline variables will be summarized by treatment group using descriptive statistics for the ITT population.

The following variables will be summarized by treatment group and overall in order to describe the study population: neonate baseline characteristics and demographics (birth weight, gestational age, sex, race, APGAR score), maternal history including the mother's age, race, medical and pregnancy history, current and pre-birth medications and delivery conditions.

The sex, GA, weight, age and age corrected for prematurity will be summarized at 24 months corrected age.

12.3.4. Efficacy variables

Need for mechanical ventilation/intubation

- Percentage of neonates needing invasive mechanical ventilation in the first 72 hours of life, in the first 28 days PNA and within 36 weeks PMA will be compared between group using the Cochran-Mantel-Haenszel (CMH) test adjusted for gestational age group. The CMH adjusted difference with its 95% CI will be presented. Additional analysis will be performed to explore the impact of use of sedation and/or analgesia.
- Percentage of neonates needing any intubation procedure, outside the initial surfactant administration period, in the first 72 hours of life, 28 days PNA and within 36 weeks PMA will be compared between treatments as need for IMV.

SpO₂

- SpO₂ will be analyzed using a linear mixed model for repeated measures (MMRM) including treatment, time point, treatment by time point interaction, and gestational age group as fixed effects and pre-procedure SpO₂ as covariate. The adjusted means in each treatment group, the adjusted mean difference between treatments and their 95% CIs at each time point and averaged over the first 120 hours post-treatment will be estimated by the model. Time profile plot of mean SpO₂ in the first 120 hours post-administration will be presented by treatment group.
- SpO₂ will be summarized by treatments on neonates still receiving respiratory support at 28±2 PNA and 36 weeks PMA by means of descriptive statistics.

FiO₂

- FiO₂ will be analyzed using a linear MMRM including treatment, time point, treatment by time point interaction, and gestational age group as fixed effects and pre-procedure FiO₂ as covariate. The adjusted means in each treatment group, the adjusted mean difference between treatments and their 95% confidence intervals (CIs) at each time point and averaged over the first 120 hours post-treatment will be estimated by the model. Time profile plot of mean FiO₂ in the 120 hours post-treatment will be presented by treatment group.
- FiO₂ will be summarized by treatments on neonates still receiving respiratory support at 28±2 PNA and 36 weeks PMA by means of descriptive statistics.

SpO₂/FiO₂ ratio

- SpO₂/FiO₂ will be analyzed using a linear MMRM including treatment, time point, treatment by time point interaction, and gestational age group as fixed

effects and pre-procedure SpO₂/FiO₂ as covariate. The adjusted means in each treatment group, the adjusted mean difference between treatments and their 95% CIs at each time point and averaged over the first 120 hours post-treatment will be estimated by the model. Time profile plot of mean SpO₂/FiO₂ in the first 120 hours post-treatment will be presented by treatment group.

- SpO₂/FiO₂ will be summarized between treatments at 28±2 Days PNA and at 36 weeks PMA by means of descriptive statistics.

Blood gas analysis

- Acid-base balance parameters (i.e. pH, pCO₂, pO₂, HCO₃, BE, lactate) will be summarized by treatments group as absolute and change from pre-treatment values by means of descriptive statistics.

Use of additional surfactant doses

- The percentage of subjects requiring at least one additional surfactant dose will be compared by treatment group by means of a Fisher's exact test at 5% significance interval. Odds ratio (OR) and related exact 95% CI will be also provided. Subjects with pulmonary hemorrhage will be excluded from this summary.
- The number of additional surfactant doses will be summarized by treatment group by means of descriptive statistics.

Duration of ventilation/oxygen supplementation (alone)

- The median duration time of invasive mechanical ventilation in the first 72 hours of life (hours), in the first 28 days PNA and within 36 weeks PMA (days), stand-alone oxygen supplementation (days), non-invasive ventilation (days) will be compared between treatment groups by using the Mann-Whitney U-test.

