6.5 Treatment allocation

A balanced block randomization scheme stratified by investigational site and gestational age group (i.e. from 25⁺⁰ to 26⁺⁶ weeks and from 27⁺⁰ to 28⁺⁶ weeks) will be prepared via a computerized system. Once the neonate’s eligibility to take part in the study is confirmed, neonates will be centrally assigned to one of the two treatment arms (LISA/Poractant alfa or ETT/Poractant alfa) through an IRT system (Interactive Response Technology, combination of voice and web response system and also referred as IVRS/IWRS). Enrollment will be staggered: the gestational age will be restricted to 27⁺⁰ to 28⁺⁶ weeks for at least the first 15 randomized neonates. After ISMB evaluation of safety data from the first 15 neonates, provided no safety concerns are raised, the enrolment will be extended to the whole population (25⁺⁰ to 26⁺⁶ weeks and from 27⁺⁰ to 28⁺⁶ weeks).

The IRT will allocate the subject to a certain treatment group using a list-based randomization algorithm and assign the unique screening number of eight digits: the country will be the first three digits (according to ISO 3166 Numeric Country Code), the investigational site number will be the second two digits and the following three digits will be the progressive numbering of the subject within each site (e.g. for the first USA site the screening numbers will be 84001001, 84001002 etc.). The IRT will also generate a confirmation after every IRT transaction is performed.

The Investigator will call the IRT on admission to receive the subject screening number and randomize the subject and obtain the medication (Poractant alfa) kit numbers. Detailed instructions for use of IRT will be provided to the site.

In the LISA group, the relevant catheter provided by the Sponsor (CHF 6440) will be dispensed and used for administration. In the control group, the endotracheal tubes available at the investigational sites for clinical practice will be used for administration.

The LISA catheter (CHF 6440) will be dispensed by the IRT system.

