12. STATISTICAL METHODS

12.1. Sample Size

No primary efficacy endpoint was defined in this study since the main objective is to describe the overall safety and efficacy profile of administering poractant alfa with two different

procedures: LISA technique or conventional administration with endotracheal tubes and brief invasive ventilation. A total of 150 neonates will be randomized in the study with a ratio 2:1 to LISA arm (i.e. 100) and conventional administration arm (i.e. 50).

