12.3.5. Safety variables

Adverse Events and Neonatal Morbidities

- Number and percent of neonates reporting AEs started during procedure for surfactant administration as well as AEs started during the procedure and judged related to the procedure will be summarized by treatment group.

For LISA group, any AE assessed as related to CHF 6440 catheter will be considered procedure-related.

These events will be also summarized by treatment group based on action required, if any (i.e. supplementary oxygen or transient increase in FiO₂, manual positive pressure ventilation, endotracheal intubation, administration of, crystalloids, or cardiopulmonary resuscitation or administration of adrenaline). The duration of endotracheal intubation and positive pressure ventilation will be

summarized as well.

A subgroup analysis of AEs during procedure for surfactant administration will be performed based on the use of sedation and/or analgesia (Yes/No).

- Incidence of AEs including neonatal complications of prematurity (see [APPENDIX III](#) for complete list), related AEs (ADRs), serious AEs (SAEs) and AEs leading to death will be summarized by treatment group both in term of frequency of neonates with at least one AE and in term of frequency of AEs (number of events). All the aforementioned categories of AEs will be summarized by System organ Class (SOC) and Preferred Term (PT).
- Frequency of neonates with major neonatal morbidities at discharge or 40 weeks PMA (whichever comes first) will be summarized by treatment group.

Vital Sign

- Vital signs parameters (SBP, DBP MBP, HR and RR) will be summarized as absolute and the change from baseline (pre-procedure) by treatment group using descriptive statistics.

Pain assessment

- PIPP score will be summarized by treatment group by means of descriptive statistics.

First administration

- Number of 1st failed attempt to insert the catheter/ETT will be summarized by treatment group. Percentage of neonates with 1st failed attempt will be compared between group using the Cochran-Mantel-Haenszel adjusted for gestational age group. The CMH adjusted difference with its 95% CI will be presented.
- Number of attempts to the first successful insertion will be summarized by treatment group by means of descriptive statistics.
- Number of device misallocation (i.e., esophageal intubation) will be summarized by treatment group by means of descriptive statistics.

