- Number of maneuvers discontinued due to neonate's severe destabilization will be summarized by treatment group by means of descriptive statistics.
- Duration of surfactant administration (min) and overall procedure for surfactant administration will be compared between treatment groups by using the Mann-Whitney U- test.

Mortality and BPD

- Death/BPD incidence at 36 weeks PMA will be compared by treatment by means of CMH test, adjusting for GA group and related 95% confidence interval will be provided.

- The incidence of BPD at 36 weeks PMA will be compared by treatment as for Death/BPD incidence.
- The mortality at 36 weeks PMA and at Day 28 will be compared by treatment as for Death/BPD incidence.
- Oxygen use at Day 28 (alone and / or during any kind of MV) will be compared by treatment as for Death/BPD incidence.

Other safety variables

- Feeding and hearing status at discharge or 40 weeks PMA (whichever comes first) will be summarized by treatment group by frequency distributions.
- Weight, OFC and length at discharge home or 40 weeks PMA will be summarized by treatment group by descriptive statistics.
- Neonates needing invasive or non-invasive respiratory support at discharge home or 40 weeks PMA will be summarized by treatment group by frequency distribution
- Neonates needing respiratory medications at discharge home or 40 weeks PMA will be summarized by treatment group by frequency distribution

Health status questionnaire at 24 months (± 3 months) corrected age

(This stand-alone assessment will be analyzed and reported separately from the main phase)

- Bayley Scales of Infant Development (cognitive and language scores) will be summarized using descriptive statistics by treatment group and BSID version (III or IV).
- Vital signs and all other variables collected through the questionnaire (i.e., anthropometric measures, cerebral palsy, seizures, feeding method, functional disability and respiratory morbidity) will be summarized by treatment group by frequency distribution or descriptive statistics, as appropriate.

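### Need for additional surfactant is the only compared proportion analysed without gestational-age adjustment: Fisher's exact test and an odds ratio where the others use stratified CMH

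*Protocol*

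**What the plan says.** Under use of additional surfactant doses, Protocol section 12.3.4 compares the percentage needing at least one further dose by a Fisher's "exact test at 5% significance interval. Odds ratio (OR) and related exact 95% CI will be also provided". The statistical methods part of the Protocol Outline says the same. Neither place mentions GA group.

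The other compared proportions are handled differently:

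- **Need for invasive mechanical ventilation** (12.3.4): "Cochran-Mantel-Haenszel (CMH) test adjusted for gestational age group. The CMH adjusted difference with its 95% CI will be presented". Need for any intubation is analysed the same way.
- **Failed first insertion attempt** (12.3.5): "Percentage of neonates with 1st failed attempt will be compared between group using the Cochran-Mantel-Haenszel adjusted for gestational age group".
- **Death/BPD** (12.3.5): "CMH test, adjusting for GA group and related 95% confidence interval will be provided". BPD, mortality and oxygen use at Day 28 follow the same method.

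Section 6.5 specifies "A balanced block randomization scheme stratified by investigational site and gestational age group". Section 12.1 states "A total of 150 neonates will be randomized in the study with a ratio 2:1 to LISA arm", with 50 in the conventional arm. Section 2.2 names need for additional doses in the secondary objective, alongside need for invasive ventilation.

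**The concern.** A choice that the protocol itself fixes departs, without explanation, from the method it uses for every comparable outcome. Two things follow.

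- **Estimate.** Need for ventilation will be reported as a GA-adjusted difference. Need for re-dosing will be reported as an odds ratio from an unstratified table. In a descriptive study the estimate and its interval are the main product, and here the two companion outcomes have no common adjusted measure.
- **Test.** Fisher's test is discrete and runs below its nominal level. Pooling over a factor that was balanced by stratified randomization lowers the true level further when that factor predicts the outcome. Both cost power.

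**Working it through.** **Inputs from the protocol:** 100 v 50 (12.1), a 5% level (12.3.4), GA group as a stratum (6.5). There is no power figure to reproduce.

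**Assumptions:** two-sided testing (sidedness is not stated); 40% of neonates in the lower GA group, so strata of 40 v 20 and 60 v 30; no exclusions for pulmonary hemorrhage. Event rates, treatment effect and GA effect are assumed as shown.

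**1. True size of Fisher's test, no GA effect.** Sum the binomial probabilities of all 100 v 50 tables with Fisher p ≤ 0.05.

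| Event rate | 10% | 20% | 30% | 40% | 50% |
|---|---|---|---|---|---|
| True size | 3.3% | 4.0% | 4.0% | 3.9% | 3.7% |

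**2. Size with a GA effect** (null rates 45% and 20% in the two GA groups, simulated). The CMH statistic is (Σ(a_k − E_k))² / ΣV_k, with E_k = m_k·n_1k/n_k and V_k = n_1k·n_2k·m_k·(n_k − m_k) / (n_k²(n_k − 1)). The corrected version replaces the numerator by (|Σ(a_k − E_k)| − 0.5)². Result: Fisher 3.3%, uncorrected CMH 5.0%. Over a wider grid Fisher's size ran from 2.4% to 4.1%; the low end needs a GA odds ratio of 5.

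**3. Power in four scenarios** (simulated).

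| Control rates, lower/higher GA | Treatment OR | Fisher | Uncorrected CMH | Gain, points | Corrected CMH |
|---|---|---|---|---|---|
| 50%/25% | 0.40 | 55.5% | 62.5% | 7.0 | 54.7% |
| 60%/25% | 0.40 | 54.2% | 63.2% | 9.0 | 55.4% |
| 30%/30% | 0.40 | 55.5% | 60.6% | 5.1 | 51.4% |
| 50%/25% | 0.25 | 87.0% | 90.0% | 3.0 | 85.8% |

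**4. Where the loss comes from.** In the first three rows an unstratified, uncorrected chi-square test has power 61.0%, 59.4% and 60.6%. Stratification alone therefore adds 62.5 − 61.0 = 1.5, 63.2 − 59.4 = 3.8 and 0 points. The rest (5.5, 5.2 and 5.1) is Fisher's conservatism.

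**5. Wider grid** (overall control rate 20 to 50%, treatment OR 0.3 to 0.6, GA OR 1 to 5).

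- The gain of uncorrected CMH over Fisher ranges from 1.6 points (control 50%, OR 0.3, no GA effect) to 11.8 points (33.5% v 45.3%; control 50%, OR 0.5, GA OR 5).
- For a GA OR of 2 to 3 it is about 2 to 8 points.
- With continuity-corrected CMH the difference from Fisher is −3.9 to +4.2 points.

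**6. Attenuation of the unadjusted odds ratio.** Take a 40% control rate (odds 0.667) and a conditional OR of 0.50. With a GA OR of 3 the treated rate is 25.8%, so the unadjusted OR is (0.258/0.742)/0.667 = 0.52. With a GA OR of 5 it is (0.268/0.732)/0.667 = 0.55.

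**The case against.** The case for leaving this alone is substantial.

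- **Fisher's test is valid.** A size below 5% means no inflated false-positive rate. A reader might infer that the result would be unsound or biased towards LISA; nothing in the protocol supports that, and the odds ratio is only slightly attenuated.
- **No decision rests on it.** The study is exploratory, with no primary efficacy endpoint and no power claim. This stands, and it limits how much the point matters.
- **The power cost is not a property of the protocol.** A reader might take one row of the table, or a band such as 5 to 9 points, as the cost. The re-dosing rate, effect, GA association and GA split are all absent from the document, and the protocol does not say whether its CMH test is continuity-corrected. Only a conditional range can be defended.
- **The missing stratum is usually the smaller part of the loss.** This also stands. It can matter as much as Fisher's conservatism when GA is a very strong predictor.
- **The percentages will be visible.** Section 12.3.1 requires number and percent for categorical variables, so a crude difference can be read off. Only the adjusted difference and its interval are missing. A reader might add that the exact interval is too wide, but no interval was computed, so that is not claimed.
- **GA adjustment is not universal.** Durations are compared by unadjusted Mann-Whitney tests. The exception holds among compared proportions only.
- **An exact test is defensible when the event rate is unknown.** That would be a fair reason, but the protocol does not give it, and it uses CMH for other outcomes, such as mortality, without giving an expected rate.

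These points reduce the weight of the concern. They do not explain the inconsistency.

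**Conclusion.** The point holds as one of consistency and modest efficiency, not validity. Need for additional surfactant is the one formally compared proportion that the protocol analyses without GA group. As a result it lacks the adjusted difference that its companion outcome, need for invasive ventilation, will have.

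Fisher's true size at 100 v 50 is about 3 to 4%. The power cost is roughly 2 to 12 points against an uncorrected CMH test, and close to nothing or reversed against a corrected one. Those figures rest on the assumed rates, effects and 40% lower-GA share, on two-sided testing, and on no exclusions. The same bullet removes neonates with pulmonary hemorrhage, so the analysed numbers may be smaller. The change is worth making because it is free and uses a method the protocol already has, but no planned conclusion depends on it.

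**What to change.** In section 12.3.4 and in the statistical methods part of the Protocol Outline, replace the Fisher sentence. Compare the percentage needing at least one additional surfactant dose by the CMH test without continuity correction, adjusted for GA group, and present the CMH adjusted difference with its 95% CI as for need for invasive mechanical ventilation. The odds ratio with exact CI may stay as a supplementary summary.

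State the absence of a continuity correction explicitly, since the gain depends on it. Fix the method in advance and do not add a rule that switches to an exact test if events turn out sparse: such a rule would make the method depend on the data. If the sponsor prefers Fisher's test, the protocol should say why this outcome differs from the others.

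Cost: one sentence in each of two places, with no new data and no change to randomization or sample size.

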6.2.3.6 Additional surfactant treatment

Up to two repeated doses could be administered at 100 mg/kg.

A second surfactant dose (poractant alfa 100 mg/kg) will be administered using the same technique as the first dose administration in case of lack of efficacy, or clinical deterioration,

as per randomization criteria ($FiO_2 \geq 0.30$ to maintain preductal oxygen saturation (SpO_2) in the target range 88–95%), within approximately 12 hours from the initial dose.

After the first and the second surfactant administration, neonates could receive a third surfactant dose (poractant alfa 100 mg/kg). If a third dose is administered, it will be provided through a standard technique. Neonates could be intubated (LISA group) or re-intubated (control group) for MV at neonatologist's discretion, if one or more of the below detailed conditions for MV in section 6.2.3.7 are satisfied.

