10.8. Recording Adverse Events

All AEs occurring during the course of the study must be documented in the Adverse Event page of the eCRF. Moreover, if the Adverse Event is serious, the Serious Adverse Event Form must also be completed.

It is responsibility of the Investigator to collect all adverse events (both serious and non-serious).

The recording period for Adverse Events is the period starting from the beginning of the procedure until the subject’s study participation ends.

Given the significant amount of possible comorbidities in the study population, any condition diagnosed before the start of the procedure will be considered a baseline condition and will be recorded in the Medical History page of the eCRF. The occurrence or worsening of these conditions during and after the study procedure must be recorded as an AE in the eCRF.

The only exception to this rule is represented by congenital anomalies including major organ malformations, genetic diseases and/or chromosomal abnormalities, that should be reported as baseline conditions even if diagnosed after treatment.

If a clinically significant abnormal laboratory finding or other abnormal assessment detected during the study period meets the definition of an AE and is not assessed as pre-existing, then the AE eCRF page must be completed, as appropriate. A diagnosis, if known, or clinical signs and symptoms if diagnosis is unknown, rather than the clinically significant abnormal laboratory finding, should be reported on the AE eCRF page. If no diagnosis is known and clinical signs and symptoms are not present, then the abnormal finding should be recorded as adverse event.

Occurrence of COVID-19 infection during the study will be reported in the Adverse Events section of the eCRF if symptoms judged related to the infection are present. Every effort should be made by the site to confirm all suspected incidences of COVID-19 in accordance with local diagnostic guidelines. Tests for detecting SARS-CoV-2 infection, as well as their results, will be reported in the eCRF. Documentation of testing and results obtained outside the clinical site, should be collected within 14 days of confirmed diagnosis (or whenever possible) and recorded in the eCRF. For all confirmed cases of COVID-19/SARS-CoV-2 the investigator must follow the standard of care in accordance with local treatment guidelines. All concomitant treatments must be recorded in the eCRF as well.

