12.2. Populations for analysis

The following populations will be considered for the analysis:

- **Intention-to-Treat population (ITT):** all randomized subjects who will receive at least one dose of study medication.
- **Safety population:** all randomized subjects who will take at least one dose of study medication.

The efficacy analyses population will be performed in the ITT population. The Safety population will be used in the analysis of all safety variables.

In case of deviation between as-randomized treatment and treatment actually received, the treatment actually received will be used in the safety analyses (i.e. an as-treated analysis will be performed).

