APPENDIX III**COMPLICATIONS OF PREMATURITY**

- **Air leaks** (pneumothorax, pneumomediastinum, pneumopericardium, pneumoperitoneum)
- **Apnea of prematurity**
- **Focal intestinal perforation (Neonatal spontaneous intestinal perforation)**
- **Germinal matrix hemorrhage/Intraventricular hemorrhage:** to be classified according to the following [28,29]:
 - Grade I - Germinal matrix hemorrhage only or germinal matrix hemorrhage plus intraventricular hemorrhage less than 10% of ventricular area.
 - Grade II – Germinal matrix hemorrhage and intraventricular hemorrhage; 10 to 50% of ventricular area.
 - Grade III - Germinal matrix hemorrhage and intraventricular hemorrhage involving more than 50% of ventricular area; lateral ventricles are usually distended.
 - Grade IV: Hemorrhagic infarction in periventricular white matter ipsilateral to intraventricular hemorrhage (also called periventricular hemorrhagic infarction).
- **Necrotizing enterocolitis**, to be classified according to modified Bell staging criteria [30,31]
- **Patent ductus arteriosus**
- **Periventricular leukomalacia**
- **Pulmonary hemorrhage**
- **Pulmonary interstitial emphysema**
- **Retinopathy of prematurity** – classification related to stage, localization and extent according to “The International Classification of Retinopathy of Prematurity Revisited” [32,33]

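### Dropping every neonate with pulmonary hemorrhage from the additional-dose comparison conditions on an event that can follow treatment

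*Protocol*

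**What the plan says.** Need for additional surfactant is part of the secondary objective (Protocol section 2.2) and is listed as an efficacy variable in section 8. Section 12.3.4 compares the percentage with at least one additional dose by Fisher's exact test at 5%, with an odds ratio and exact 95% CI. It then states: "Subjects with pulmonary hemorrhage will be excluded from this summary". The synopsis repeats the sentence. Neither place gives an onset window, a severity threshold or a reason.

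Other parts of the protocol bear on this:

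- Section 12.2: "The efficacy analyses population will be performed in the ITT population". That population is defined as randomised neonates given at least one dose, with no exception for hemorrhage.
- Appendix III lists "Pulmonary hemorrhage" among the complications of prematurity. Section 7.1 has these recorded among adverse events.
- Section 10.8: "The recording period for Adverse Events is the period starting from the beginning of the procedure", and it runs to the end of study participation.
- Section 12.3.5 summarises by arm the "Incidence of AEs including neonatal complications of prematurity".
- Section 4.3 does not list pulmonary hemorrhage as an exclusion criterion.
- Section 6.2.3.6 provides for a second dose "in case of lack of efficacy, or clinical deterioration", within about 12 hours of the first. Section 6.2.3.7 applies the criteria for intubation and further doses in the first 72 hours of life.
- The next line of section 12.3.4 carries no exclusion: "The number of additional surfactant doses will be summarized by treatment group by means of descriptive statistics".

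**The concern.** A neonate leaves this comparison because of something that can occur after randomisation and after the assigned procedure, and that the trial itself treats as a safety outcome to be compared descriptively by arm. Randomisation then no longer protects the comparison: the neonates who remain are selected by an event that the procedure may influence.

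The missing time limit makes this worse. The redosing criteria operate in the first hours and days, while adverse events are collected until the end of participation. As written, a hemorrhage weeks later removes a neonate whose redosing status was already settled. The rule also drops the neonate and not merely a dose, so it removes hemorrhage cases that were never redosed as well as those redosed earlier for another reason.

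Because redosing follows lack of efficacy or deterioration, a link between hemorrhage and redosing is plausible. If there is one, and hemorrhage is more frequent in one arm, that arm will appear to need fewer extra doses than it did.

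**Working it through.** The protocol states no redosing rate, hemorrhage rate, effect size or power for this variable, so there is no figure of its own to reproduce. The only inputs taken from it are the arm sizes in section 12.1: 100 LISA and 50 conventional, 150 in total. **All rates below are assumptions chosen to show the range.**

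**Formula.** In an arm of n neonates with r redosed and h with hemorrhage, of whom a share q is redosed, the percentage after exclusion is (r − q·h)/(n − h). The odds ratio is LISA against control.

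**No true difference.** Take r = 30/100 and 15/50, so the all-ITT odds ratio is 1.00. For hemorrhage 4 versus 5:

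- q = 1: LISA (30 − 4)/(100 − 4) = 26/96 = 27.1%; control (15 − 5)/(50 − 5) = 10/45 = 22.2%; OR = (26/70)/(10/35) = 1.30.
- q = 0.3: 28.8/96 and 13.5/45, both 30%; OR = 1.00.
- q = 0: 30/96 and 15/45; OR = (30/66)/(15/30) = 0.91.

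| Hemorrhage, LISA vs control | q = 1.0 | q = 0.6 | q = 0.3 | q = 0 |
|---|---|---|---|---|
| 4/100 vs 5/50 | 1.30 | 1.11 | 1.00 | 0.91 |
| 8/100 vs 2/50 | 0.85 | 0.93 | 1.00 | 1.06 |
| 6/100 vs 3/50 | 1.00 | 1.00 | 1.00 | 1.00 |

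Fisher's p at q = 1 is 0.68 for the first row and 0.69 for the second (22/92 vs 13/48), so neither produces a false positive. In the third row at q = 1 the odds ratio is unaffected, but both percentages fall from 30% to 24/94 = 12/47 = 25.5%.

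**A true difference.** Suppose 30/100 versus 25/50 are redosed in the ITT set: OR 0.43, p = 0.020. Remove 3 LISA and 5 control neonates with hemorrhage, all redosed, and this becomes 27/97 versus 20/45: OR 0.48, p = 0.057. For true rates of 30% versus 50%, exact power of the Fisher test is 63% in the ITT set and 45% after that exclusion.

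**Denominators.** In the 4 versus 5 example the percentage rests on 96 + 45 = 141 neonates. Read literally, the number-of-doses summary in the next line rests on 150, if all randomised neonates are dosed.

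**Choice of test (secondary).** Allocation is "stratified by investigational site and gestational age group", and the other between-arm comparisons of percentages in sections 12.3.4 and 12.3.5 use a CMH test adjusted for gestational age group. Simulation under no effect (gestational age strata 40:60; assumed redosing 45%/20%, 60%/25% and 30%/30%; 20,000 runs each) gave a type I error of 2.8–4.1% for Fisher and 4.9–5.1% for CMH.

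**The case against.** The strongest reply is that section 12.2 is a general rule and the hemorrhage sentence a specific, prespecified exception, so the two can be read together. The ITT set is in any case a modified one, since it requires a dose. That weakens the charge of contradiction but not the main point: a prespecified exclusion based on a post-treatment event is still a selection made after randomisation.

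The sponsor may also want to measure redosing apart from hemorrhage. That would be a legitimate question, but the protocol does not state it, and removing the whole neonate with no time limit does not answer it. An SAP could add a window, but the protocol already fixes the unlimited rule in two places.

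Several limits do stand. The link between hemorrhage and redosing is assumed: section 6.2.3.6 does not mention hemorrhage, and the bias disappears or changes sign under other assumptions in the table. More extreme assumptions move a null odds ratio further, but they need hemorrhage cases to make up most of one arm's redosing, so I do not rely on them. The different denominators may be loose drafting, if the sentence was meant to cover both lines, and call only for clarification. Fisher's test is valid, merely conservative. Hemorrhage is reported by arm, so an imbalance would be visible, although that does not repair the estimate.

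**Conclusion.** The concern holds. The protocol fixes an open-ended exclusion, based on an event that can follow treatment, in a formally tested efficacy comparison that it otherwise assigns to the ITT population. That reading of the text is firm.

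The size and direction of the effect are not known. On the assumed rates in the main table, a true odds ratio of 1.00 moves to between 0.85 and 1.30; in a separate assumed example a p-value moves from 0.020 to 0.057. There is no distortion of the odds ratio if hemorrhage rates and their link to redosing are the same in both arms, or if hemorrhage cases are redosed at the background rate in these null examples.

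The study is exploratory with no primary efficacy endpoint, so the consequence is a distorted estimate of one secondary efficacy variable. It should be corrected, but it does not threaten the main safety objective.

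**What to change.** Delete the exclusion sentence from section 12.3.4 and from the statistical methods in the synopsis, and from the SAP if it is repeated there. State that the percentage with at least one additional dose is analysed in all ITT neonates, counting every additional dose given whatever its presumed reason, and that the number of doses uses the same denominator.

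If the hemorrhage-excluded result is still wanted, present it as a labelled sensitivity analysis, with hemorrhage counts by arm and their timing relative to redosing.

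As an optional improvement in the same edit, replace the unstratified Fisher test with the CMH test adjusted for gestational age group, with the adjusted difference and 95% CI, to match the other compared percentages.

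The cost is one sentence removed in two places. The main analysis needs no new data. The timing listing uses adverse-event onset and dose times, provided that the eCRF holds them.
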